7.4 Dosage Modification

7.4.1 Dose Delay Criteria for Cohorts A, B, and C

Nivolumab and ipilimumab administration should be delayed for the following:

- Grade 2 non-skin, drug-related AE, except for fatigue
- Grade 3 skin, drug-related AE
- Grade 2 drug-related creatinine, AST, ALT and/or total bilirubin abnormalities
- Grade ≥ 3 drug-related laboratory abnormality, with the following exceptions:
 - Grade 3 lymphopenia or asymptomatic amylase or lipase does not require a dose delay
 - Grade ≥ 3 AST, ALT, Total Bilirubin will require dose discontinuation
- Any AE, laboratory abnormality or inter-current illness which, in the judgment of the investigator, warrants delaying the dose of study medication.
- Participants receiving ipilimumab in combination with nivolumab that have drug-related toxicities that meet the criteria for dose delay, should have both drugs (ipilimumab and nivolumab) delayed until retreatment criteria are met. (Exceptions apply to the retreatment criteria after dose delay of ipilimumab and nivolumab for Grade 4 amylase and lipase abnormalities that are not associated with symptoms or clinical manifestations of pancreatitis and that are attributed to ipilimumab alone.)

Participants who require delay should be re-evaluated weekly or more frequently if clinically indicated and resume study medication dosing when re-treatment criteria are met.

Rescheduling:

- Nivolumab may be delayed until the next planned ipilimumab dose if the next ipilimumab dose is scheduled within the next 12 days. This will permit periodic ipilimumab dosing to be synchronized with nivolumab dosing.

- Ipilimumab should be dosed at the specified interval regardless of any delays in intervening nivolumab doses. However, in order to maintain periodic synchronized dosing of ipilimumab and nivolumab, the dosing days of nivolumab and ipilimumab may be adjusted within the permitted ± 5 day window, as long as consecutive nivolumab doses are given at least 12 days apart. Ipilimumab may be delayed beyond the 5 day window if needed to synchronize with the next nivolumab dose.
- If an ipilimumab dose is delayed beyond 6 weeks from the prior ipilimumab dose, then subsequent ipilimumab doses should be rescheduled to maintain the 6 week interval between consecutive ipilimumab doses.
- A dose delay of ipilimumab which results in no ipilimumab dosing for > 12 weeks requires ipilimumab discontinuation, with exceptions as noted in [Section 8.1.1.2](#).

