7.4.5 Criteria to Resume Dosing

7.4.5.1 Criteria to Resume Nivolumab for Cohorts A, B, and C

Participants may resume treatment with nivolumab when the drug-related AE(s) resolve(s) to Grade \leq 1 or baseline, with the following exceptions:

- Participants may resume treatment in the presence of Grade 2 fatigue.
- Participants who have not experienced a Grade 3 drug-related skin AE may resume treatment in the presence of Grade 2 skin toxicity.
- Participants with baseline Grade 1 AST/ALT or total bilirubin who require dose delays for reasons other than a 2-grade shift in AST/ALT or total bilirubin may resume treatment in the presence of Grade 2 AST/ALT OR total bilirubin.
- Participants with combined Grade 2 AST/ALT and total bilirubin values meeting discontinuation parameters ([Section 8.1](#)) should have treatment permanently discontinued.
- Drug-related pulmonary toxicity, diarrhea, or colitis must have resolved to baseline before treatment is resumed. Participants with persistent Grade 1 pneumonitis after completion of a

steroid taper over at least 1 month may be eligible for retreatment if discussed with and approved by the BMS Medical Monitor.

- Participants who received systemic corticosteroids for management of any drug-related toxicity must be off corticosteroids or have tapered down to an equivalent dose of prednisone ≤ 10 mg/day.

Participants with drug-related endocrinopathies adequately controlled with only physiologic hormone replacement may resume treatment after consultation with the BMS Medical Monitor (or designee). Adrenal insufficiency requires discontinuation regardless of control with hormone replacement.

Dose delay of nivolumab which results in treatment interruption of > 6 weeks requires treatment discontinuation, with exceptions as noted in [Section 8.1.1](#).

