7.4.5.2 Criteria to Resume Ipilimumab for Cohorts A, B, and C

Participants may resume treatment with nivolumab and ipilimumab when drug-related AE(s) resolve(s) to Grade 1 or baseline value, with the following exceptions:

- Participants may resume treatment in the presence of Grade 2 fatigue.
- Participants who have not experienced a Grade 3 drug-related skin AE may resume treatment in the presence of Grade 2 skin toxicity.
- Participants with baseline Grade 1 AST/ALT or total bilirubin who require dose delays for reasons other than a 2-grade shift in AST/ALT or total bilirubin may resume treatment in the presence of Grade 2 AST/ALT or total bilirubin.
- Participants with combined Grade 2 AST/ALT and total bilirubin values meeting discontinuation parameters ([Section 8.1](#)) should have treatment permanently discontinued.
- Drug-related pulmonary toxicity, diarrhea, or colitis must have resolved to baseline before treatment is resumed.
- Participants who received systemic corticosteroids for management of any drug-related toxicity must be off corticosteroids or have tapered down to an equivalent dose of prednisone ≤ 10 mg/day.
- Drug-related endocrinopathies (except Grade 3 or greater adrenal insufficiency) adequately controlled with only physiologic hormone replacement may resume treatment after consultation with the BMS Medical Monitor
- Dose delay of ipilimumab which results in no ipilimumab dosing for > 12 weeks requires ipilimumab discontinuation, with exceptions as noted in [Section 8.1.1.2](#).
- Ipilimumab may not be resumed sooner than 37 days after the prior ipilimumab dose.
- In general, participants who meet criteria to resume ipilimumab will also have met criteria to resume nivolumab, so it should be feasible to synchronize dosing of both drugs when resuming ipilimumab. In order to facilitate this, the dosing days of nivolumab and ipilimumab may be adjusted within the permitted ± 5 day window, as long as consecutive nivolumab doses are given at least 12 days apart.

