One exception to note is when ipilimumab and nivolumab doses are delayed due to drug-related Grade 4 amylase or lipase abnormalities not associated with symptoms or clinical manifestations of pancreatitis. If the investigator assesses the Grade 4 amylase or lipase abnormality to be related to ipilimumab and not related to nivolumab, nivolumab may be resumed when the amylase or lipase abnormality resolves to Grade ≤ 3 but ipilimumab may only be resumed when the amylase or lipase abnormality resolves to Grade 1 or baseline. Investigator attribution of this toxicity to the ipilimumab dosing must be clearly noted in the participant's medical chart. The BMS Medical Monitor should be consulted prior to resuming nivolumab in such participants.

See [Section 8](#) for treatment discontinuation criteria.

Please see [Section 7.4.5.3](#) Criteria to Resume Nivolumab or Ipilimumab for Special Population.

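### For controlled Grade 2 adrenal insufficiency, section 7.4.5.1 requires nivolumab to stop whatever the grade, while 7.4.5.2 lets both drugs resume below Grade 3

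*Combined protocol and SAP*

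**What the plan says.** **Hold (7.4.1).** The triggers for delaying dosing include "Grade 2 non-skin, drug-related AE, except for fatigue". When a toxicity meets a delay criterion, both drugs are held until the retreatment criteria are satisfied.

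**Resuming nivolumab (7.4.5.1).** A drug-related endocrinopathy controlled by physiologic hormone replacement alone may resume after Medical Monitor consultation. No grade is given. The next sentence is: "Adrenal insufficiency requires discontinuation regardless of control with hormone replacement". It gives no grade either.

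**Resuming ipilimumab (7.4.5.2).** The heading names ipilimumab, but the opening sentence reads "Participants may resume treatment with nivolumab and ipilimumab when drug-related AE(s) resolve(s) to Grade 1 or baseline value", followed by exceptions. One exception is "Drug-related endocrinopathies (except Grade 3 or greater adrenal insufficiency) adequately controlled with only physiologic hormone replacement may resume treatment", again after Medical Monitor consultation. The section adds that, in general, "participants who meet criteria to resume ipilimumab will also have met criteria to resume nivolumab". It closes by referring to Section 8 "for treatment discontinuation criteria".

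**Discontinuation (8.1.1.1 and 8.1.1.2).** Section 8.1.1.1 repeats the adrenal sentence inside its item on Grade 3 endocrinopathies, and separately forbids ipilimumab once nivolumab has been discontinued. Section 8.1.1.2 mentions adrenal insufficiency only as a carve-out within its Grade 3 criterion.

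**Cohort A1 (7.4.5.3 and 8.1.1.3).** These adopt the same rules. Their listed exceptions cover liver tests and, in 8.1.1.3, renal dysfunction; none concerns adrenal insufficiency.

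**The concern.** Take a participant with drug-related Grade 2 adrenal insufficiency who is stable on replacement. Under 7.4.5.1 nivolumab ends for good, and ipilimumab ends with it. Under 7.4.5.2 both drugs may restart after a consultation. Which section is opened first therefore decides the whole regimen.

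An error in either direction has a cost: further exposure to both drugs after an event that one section treats as a required stop, or permanent loss of study treatment in metastatic lung cancer. The event is foreseeable, since 10.3.2 lists adrenal insufficiency among the endocrine immune-mediated events. The study has no data monitoring committee (5.1.2), so consistent handling depends more heavily on the written dosing rules.

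**Working it through.** No formula applies. The check follows one case through the sections.

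**Step 1. Does the case reach the resume rules?** Yes. Adrenal insufficiency is a non-skin event, so at Grade 2 section 7.4.1 holds both drugs.

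**Step 2. What does each section say?**

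| Section | Grade attached to adrenal insufficiency | Controlled Grade 2 case |
|---|---|---|
| 7.4.5.1 (resume nivolumab) | None | Discontinue nivolumab |
| 7.4.5.2 (resume; opening covers both drugs) | Grade 3 or above | Both may resume after consultation |
| 8.1.1.1 (discontinue nivolumab) | None in the sentence; it sits in a Grade 3 item | Not named |
| 8.1.1.2 (discontinue ipilimumab) | Grade 3, from the criterion that contains it | Not named |

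One of the two resume sections stops treatment and the other permits it. Neither discontinuation section names Grade 2 adrenal insufficiency, leaving only their general clauses, such as investigator judgement or prolonged delay.

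**Step 3. What follows for the second drug?** If nivolumab stops under 7.4.5.1, 8.1.1.1 bars ipilimumab. The choice is therefore both drugs or neither.

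**Step 4. Is the difference presented as drug-specific?** Not in 7.4.5.2. That section expects participants who qualify for ipilimumab to qualify, in general, for nivolumab. The exception it then sets out begins "One exception to note is when ipilimumab and nivolumab doses are delayed due to drug-related Grade 4 amylase or lipase abnormalities", and there nivolumab may restart earlier than ipilimumab. For adrenal insufficiency nivolumab would be the more restricted drug, and no reason is given.

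**Step 5. Other grades.** At Grade 3 and above both resume sections withhold treatment, so they agree. The Grade 4 endocrinopathy exceptions in 8.1.1.1 and 8.1.1.2 do not repeat the adrenal carve-out, but both resume sections already prevent resumption there.

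**Step 6. How many participants do the rules govern?** From 5.2.1, planned treated participants in Cohorts A, B and C are 400 + 400 + 100 = 900. Adding Cohort A1 gives 900 + 200 = 1,100. These are numbers governed by the text. The documents give no incidence of adrenal insufficiency, so no affected count can be derived.

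**The case against.** The strongest reply is that a careful reader can reach an answer. Section 7.4.5.1 is the nivolumab section and its adrenal sentence is mandatory; 7.4.5.2 is headed for ipilimumab and only permits. A permission need not override a stop, and once nivolumab stops ipilimumab follows. **This stands in part.** A reader might infer that the protocol leaves sites with no workable rule, and that goes too far: the conservative reading gives a definite result. But it has to set aside the mention of nivolumab in the opening sentence of 7.4.5.2, and it leaves little or no use for the permission below Grade 3. The permission might keep some content where the event is attributed to ipilimumab alone, because 8.1 assesses the drugs separately. The adrenal sentence in 7.4.5.1 says nothing about attribution, so that reading is possible but not established.

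A reader might also infer from the table that Grade 3 was the intended threshold, since three of the four statements are linked to it. The documents do not support that. In 8.1.1.1 the link is by position only; the sentence is the same as in 7.4.5.1 and carries no grade. Grouped by drug, the sentence is ungraded in both nivolumab sections and the exclusion is tied to Grade 3 in both ipilimumab sections. Adding a Grade 3 limit to 7.4.5.1 on placement alone would loosen a nivolumab safety stop.

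Nor can it be said that the Medical Monitor has only these conflicting texts. Section 7.4.4 refers to management algorithms that are also in the Investigator Brochures. The endocrinopathy algorithm in Appendix 8 is a figure not reproduced in the text reviewed, and it may give the threshold. Consultation with the Monitor, and the requirement in Section 9 to discuss immediate safety concerns with the sponsor, also limit divergence between sites. These points lower the practical risk; they do not reconcile the two resume sections.

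**Conclusion.** The inconsistency is real and confined to one case: drug-related Grade 2 adrenal insufficiency controlled on physiologic hormone replacement. As written, 7.4.5.1 ends nivolumab, and through 8.1.1.1 ipilimumab, while 7.4.5.2 permits both to resume. Section 8 does not choose between them. It should be corrected because the outcomes are opposite for the same participant and the correction is small.

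The conclusion rests on the current wording and on taking the opening sentence of 7.4.5.2 at face value. Confidence is high that the texts conflict; which threshold was intended cannot be determined from the text reviewed.

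A reader might look for a consequence for the trial's results. None is claimed: the primary endpoint counts Grade 3-4 and Grade 5 events, so a Grade 2 event does not enter it, and no sample size, estimate or other statistical figure is involved. The point concerns participant safety and uniform dosing.

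**What to change.** 1. Confirm the intended grade threshold against the endocrinopathy algorithm and both Investigator Brochures.
2. State that threshold in the same terms in 7.4.5.1 and 7.4.5.2. If the stop applies at any grade, remove the Grade 3 qualifier from 7.4.5.2 and state the any-grade stop in 8.1.1.1 and 8.1.1.2 as well. If it applies only from Grade 3, add that limit to 7.4.5.1, but only once the source documents confirm it.
3. Until this is settled, instruct sites to follow the stricter stop in 7.4.5.1.
4. Optional tidying: repeat the adrenal carve-out in the Grade 4 endocrinopathy exceptions of 8.1.1.1 and 8.1.1.2. This changes little, since resumption is already withheld at that grade.

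The cost is a few words in two to four sections and a notice to sites, with no added visits or procedures. Cohort A1 inherits the change by reference. The real cost is clinical and depends on the threshold: an any-grade stop permanently ends both drugs for participants whose Grade 2 adrenal insufficiency is controlled, while a Grade 3 threshold keeps them eligible to resume after Medical Monitor consultation. The interim instruction carries the first of these costs while it is in force.

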7.4.5.2 Criteria to Resume Ipilimumab for Cohorts A, B, and C

Participants may resume treatment with nivolumab and ipilimumab when drug-related AE(s) resolve(s) to Grade 1 or baseline value, with the following exceptions:

- Participants may resume treatment in the presence of Grade 2 fatigue.
- Participants who have not experienced a Grade 3 drug-related skin AE may resume treatment in the presence of Grade 2 skin toxicity.
- Participants with baseline Grade 1 AST/ALT or total bilirubin who require dose delays for reasons other than a 2-grade shift in AST/ALT or total bilirubin may resume treatment in the presence of Grade 2 AST/ALT or total bilirubin.
- Participants with combined Grade 2 AST/ALT and total bilirubin values meeting discontinuation parameters ([Section 8.1](#)) should have treatment permanently discontinued.
- Drug-related pulmonary toxicity, diarrhea, or colitis must have resolved to baseline before treatment is resumed.
- Participants who received systemic corticosteroids for management of any drug-related toxicity must be off corticosteroids or have tapered down to an equivalent dose of prednisone ≤ 10 mg/day.
- Drug-related endocrinopathies (except Grade 3 or greater adrenal insufficiency) adequately controlled with only physiologic hormone replacement may resume treatment after consultation with the BMS Medical Monitor
- Dose delay of ipilimumab which results in no ipilimumab dosing for > 12 weeks requires ipilimumab discontinuation, with exceptions as noted in [Section 8.1.1.2](#).
- Ipilimumab may not be resumed sooner than 37 days after the prior ipilimumab dose.
- In general, participants who meet criteria to resume ipilimumab will also have met criteria to resume nivolumab, so it should be feasible to synchronize dosing of both drugs when resuming ipilimumab. In order to facilitate this, the dosing days of nivolumab and ipilimumab may be adjusted within the permitted ± 5 day window, as long as consecutive nivolumab doses are given at least 12 days apart.

One exception to note is when ipilimumab and nivolumab doses are delayed due to drug-related Grade 4 amylase or lipase abnormalities not associated with symptoms or clinical manifestations of pancreatitis. If the investigator assesses the Grade 4 amylase or lipase abnormality to be related to ipilimumab and not related to nivolumab, nivolumab may be resumed when the amylase or lipase abnormality resolves to Grade ≤ 3 but ipilimumab may only be resumed when the amylase or lipase abnormality resolves to Grade 1 or baseline. Investigator attribution of this toxicity to the ipilimumab dosing must be clearly noted in the participant's medical chart. The BMS Medical Monitor should be consulted prior to resuming nivolumab in such participants.

See [Section 8](#) for treatment discontinuation criteria.

Please see [Section 7.4.5.3](#) Criteria to Resume Nivolumab or Ipilimumab for Special Population.

7.4.5.3 Criteria to Resume Nivolumab and Ipilimumab for Special Population (Cohort A1)

The criteria to resume nivolumab and ipilimumab dosing described in [Section 7.4.5.1](#) and [Section 7.4.5.2](#) apply to special population participants, with the following exceptions for hepatic impairment:

- Participants with Grade 2 baseline AST or ALT elevation (> 3.0 - $5.0 \times$ ULN), who require dose delays for reasons other than drug-related AST or ALT elevation $> 8 \times$ ULN, may resume dosing in the presence of AST or ALT elevation $\leq 8 \times$ ULN.
- Participants with Grade 2 baseline total bilirubin (> 1.5 - $3.0 \times$ ULN), who require dose delays for reasons other than drug-related total bilirubin elevation $> 5.0 \times$ ULN, may resume dosing in the presence of total bilirubin elevation $\leq 5.0 \times$ ULN.

Participants with combined AST/ALT and total bilirubin values meeting discontinuation parameters ([Section 8.1](#)) should have treatment permanently discontinued.

7.5 Preparation/Handling/Storage/Accountability

The investigational product should be stored in a secure area according to local regulations. It is the responsibility of the investigator to ensure that investigational product is only dispensed to study Participants. The investigational product must be dispensed only from official study sites by authorized personnel according to local regulations.

The product storage manager should ensure that the study treatment is stored in accordance with the environmental conditions (temperature, light, and humidity) as determined by BMS. If concerns regarding the quality or appearance of the study treatment arise, the study treatment should not be dispensed and contact BMS immediately.

Study treatment not supplied by BMS will be stored in accordance with the package insert.

Investigational product documentation (whether supplied by BMS or not) must be maintained that includes all processes required to ensure drug is accurately administered. This includes documentation of drug storage, administration and, as applicable, storage temperatures, reconstitution, and use of required processes (eg, required diluents, administration sets).

- Required storage conditions for nivolumab and ipilimumab are provided in [Table 7-1](#).
- Further guidance on preparation of nivolumab and ipilimumab for infusion will be provided in a separate Pharmacy Manual.

Further guidance and information for final disposition of unused study treatment are provided in [Appendix 2](#).

7.5.1 Retained Samples for Bioavailability / Bioequivalence

Not Applicable.

7.6 Treatment Compliance

Study treatment compliance will be periodically monitored by drug accountability. Drug accountability should be reviewed by the site study staff at each visit to confirm treatment compliance. Sites should discuss discrepancies with the participant at each on-treatment study visit.

7.7 Concomitant Therapy

7.7.1 Prohibited and/or Restricted Treatments

Prohibited and/or restricted medications taken prior to study drug administration in the study are described below. Medications taken within 14 days prior to study drug administration must be recorded on the CRF.

The following medications are prohibited during the study (unless utilized to treat a drug related AE):

- Immunosuppressive agents
- Immunosuppressive doses of systemic corticosteroids (except as stated in Section 7.7.2)
- Any concurrent anti-neoplastic therapy (ie, chemotherapy, hormonal therapy, immunotherapy, extensive, non-palliative radiation therapy, or standard or investigational agents for treatment of the disease under study). Allowable palliative radiation is described in [Section 7.7.2.1](#).
- Any botanical preparation (eg herbal supplements or traditional Chinese medicines) intended to treat the disease under study or provide supportive care. Use of marijuana and its derivatives for treatment of symptoms related to cancer or cancer treatment are permitted if obtained by medical prescription or if its use (even without a medical prescription) has been legalized locally.

Any concomitant therapies taken at any time during the study must be recorded on the CRF.

7.7.2 Other Restrictions and Precautions

Participants with a condition requiring systemic treatment with either corticosteroids (> 10 mg daily prednisone equivalent) or other immunosuppressive medications within 14 days of treatment assignment are excluded. Inhaled or topical steroids, and adrenal replacement

steroid doses > 10 mg daily prednisone equivalent, are permitted in the absence of active autoimmune disease.

7.7.2.1 Palliative Radiotherapy (All Cohorts)

On study palliative radiotherapy is not allowed on target lesions used to assess disease response and designated as such in the eCRF. Non-target bone lesions not so designated and that do not include lung tissue in the planned radiation field may be treated with palliative radiotherapy at any time while participants remain on study treatment. In addition, palliative radiotherapy to a single metastatic site, other than bone, is permitted in participants who do not require immediate initiation of second line systemic anti-cancer therapy. Such radiotherapy to non-bone lesions must not be given within 2 weeks of initiation of study therapy and such lesions are not permitted to be designated as baseline target lesions in the eCRF. Details of palliative radiotherapy should be documented in the source records and CRF. Details in the source records should include: dates of treatment, anatomical site, dose administered and fractionation schedule, and AEs.

Participants requiring palliative radiotherapy to designated target lesions must be discontinued from study therapy. Participants requiring palliative radiotherapy should be carefully assessed for disease progression. Participants considered as having progressive disease are required to discontinue study therapy, unless eligible to continue treatment beyond progression per the guidance in [Section 8.1.2](#).

